3.3.1.2.1. Planned Dose Levels

Prior to the start of the study, projected dose levels on Schedule 1 (in mg/kg) are 0.03, 0.06, 0.12, 0.24, 0.48, 0.96, 1.92, 2.8, 3.6, and 4.5 mg/kg; actual dose levels will be determined by N-CRM (Neuenschwander-Continuous Reassessment Method). Additional doses and schedules may be explored based on emerging safety, PK, and PD data. The maximum dose to be administered in this trial will not exceed 5 mg/kg.

Description of the New Continuous Reassessment Method: After each cohort, a dosing recommendation for the next cohort will be made using the N-CRM [Neuenschwander, 2008]. All available data, including safety, PK and PD data from current and prior cohorts will be reviewed at the dose escalation meeting (see Section 12.1). Although the N-CRM will be used to recommend the next dosing level, clinical judgment by the Medical Monitor and internal dose-escalation committee in consultation with the investigators can halt enrolment into lower dose cohorts as deemed appropriate at any time during the trial.

The N-CRM design is a type of Bayesian adaptive dose escalation scheme that assumes a two-parameter logistic model for the toxicity rate based on dose. It is a modified version of the original Continuous Reassessment Method [O'Quigley, 1990]. A CRM-based design uses a statistical model for dose and toxicity, and is expected to locate the MTD efficiently while minimizing the number of subjects exposed to pharmacologically inactive dose levels.

The method is fully adaptive and makes use of all the DLT information available at the time of each dose assignment. In contrast, the 3+3 method only uses information from one dosing cohort at a time.

At the time of each dose escalation decision, the Fixed and Adaptive Clinical Trial Simulator (FACTS) will be used to obtain, for each potential dose, the posterior probabilities that the DLT rate for that dose lies in each of four toxicity intervals (under dosing, target dose range, excessive toxicity, and unacceptable toxicity). The four DLT toxicity intervals are defined as follows:

- [0%, 16%) Underdosing
- [16%, 33%) Target toxicity
- [33%, 60%) Excessive toxicity

- [60%, 100%) Unacceptable toxicity

The recommended dose will be the dose with the highest posterior probability of lying in the target toxicity interval with the additional requirement that the sum of the posterior probabilities of the DLT rate lying in the excessive toxicity or unacceptable toxicity range is less than 25%. Selection of the next dose cohort to be enrolled is also subject to the constraint that the next dose level can be no more than two times that of the current dose level. An updated estimate of the toxicity curve will be provided at the time of each dose escalation meeting (see Section 12.1).

Note that de-escalation as well as escalation is possible using this method.

Dose escalation will continue until:

- i) Six subjects have been treated at the current target dose

AND

For the current dose level, the posterior probabilities of the DLT rate lying within the excessive toxicity interval or within the unacceptable toxicity interval sum to less than 25%.

AND

For the next higher dose, the posterior probabilities of the DLT rate lying within the excessive toxicity interval or within the unacceptable toxicity interval sum to less than 25%.

OR

- ii) No doses are usable (i.e. For ALL doses, the posterior probabilities of the DLT rate lying within the excessive toxicity interval or within the unacceptable toxicity interval sum to more than 25%)

AND

At least two DLTs have been observed.

The N-CRM model used to determine the MTD for Schedule 1 will utilize a single subject/cohort run-in phase.

3.3.1.2.2. Implementation of N-CRM

The N-CRM model implementation will be performed using Fixed and Adaptive Clinical Trial Simulator (FACTS) (Version 2.3 or higher) from Tessella.

3.3.1.2.3. Bayesian Prior

The N-CRM methodology requires that a Bayesian prior for the toxicity curve be pre-specified.

The proposed prior probabilities of DLT are an approximation on the potential toxicity profile based on the available non clinical toxicology package, dosing range being considered, and literature data available from clinical trials with other ADCs. Additionally, the prior is considered a ‘weakly informative prior’ and is defined with a fairly wide credible interval. This allows the model the freedom to estimate the observed probabilities of toxicity with minimal restriction.

[figure not shown]
The initial Bayesian prior used for this design is determined by using the quantile method. For each dose, an estimate of the median probability of DLT was specified, along with a 95% credible interval. The 95% credible intervals are intentionally wide due to limited information about the toxicity profile of GSK2857916 in humans. [Table 5](#) shows the median prior probability of experiencing a DLT at the given dose along with a 95% credible interval around the median:

Table 5 Table of Specified Prior Probability of DLT (with 95% Credible Interval)

Anticipated Dose (mg/kg)	2.5% Quantile for Probability of Toxicity	Median Probability of Toxicity	97.5% Quantile for Probability of Toxicity
0.03	0	0.001	0.80
0.06	0.01	0.02	0.82
0.12	0.02	0.05	0.84
0.24	0.03	0.1	0.86
0.48	0.05	0.15	0.88
0.96	0.07	0.2	0.90
1.92	0.1	0.225	0.92
2.8	0.11	0.275	0.94
3.6	0.12	0.35	0.96
4.5	0.13	0.425	0.98

A graphical presentation of the initial prior is displayed in [Figure 1](#). Doses are the projected doses. Actual doses used during the conduct of the trial may vary. An intermediate prior will be derived based on the initial prior by FACTS (Version 2.3 or higher) from Tessella. The final prior is determined based on the intermediate prior and all available data.

Figure 1 Graphical display of the prior distribution for the probability of DLT given dose

3.3.2. Dose Escalation on Schedule 2 (GSK2857916 administered once weekly x3, 1 week rest; 28 days = 1 cycle)

(Note: For details on scheduled procedures in subjects given GSK2857916 on Schedule 2 in Part 1, refer to Time and Events Table in Section 7.1.1.2)

The MTD (MTD1) or RP2D (RP2D1) established for GSK2857916 on Schedule 1 i.e., once every three weeks schedule, will inform selection of the starting dose for Schedule 2 i.e., the once weekly schedule. Additional cohort(s) may be enrolled to evaluate the safety, PK, and PD of GSK2857916 for the once weekly dosing schedule to establish an MTD2. GSK2857916 will be dosed once weekly for 3 consecutive weeks, followed by 1 week off (Schedule 2 = 28-day cycle).

- The once weekly dosing cohorts may be explored prior to, or in parallel with, enrollment to the expansion cohorts (Part 2).
- The dose escalation of the once weekly schedule will utilize a separate N-CRM model from the model used for the once every three week schedule. The information gained from the evaluation of the once every three week schedule (Schedule 1) will be utilized to more accurately define the N-CRM model used for dose escalation on the once weekly schedule (Schedule 2).
- Depending on emerging safety signals, the proposed weekly starting dose will be 25% of MTD1 or RP2D1. If the initial dose of 25% of MTD1 or RP2D1 is not tolerated, dose escalation on the weekly schedule will be terminated and enrollment into Schedule 2 will be closed. If the starting dose is tolerated, escalation on the weekly schedule will continue at increments of $\leq 30\%$ and will follow the N-CRM procedure until MTD2 or RP2D2 is reached.
- The MTD will be defined as that dose which has the highest probability of having a DLT rate within the target toxicity interval and for which the probability that the

DLT rate lies within the excessive toxicity or the unacceptable toxicity window is less than 25% (see Section 3.3.3 for DLT definitions). The DLT assessment period on Schedule 2 will be 28 days.

- The N-CRM procedure for the weekly schedule will not utilize a single subject/cohort run-in phase. Schedule 2 dose escalation cohorts will consist of 3 or more subjects due to higher starting dose and greater probability of toxicity.
- Dose escalation decisions will also take into account all available data. This includes, but is not limited to the safety and PK characteristics of all cohorts assessed. In addition, dose escalation decisions will be determined by the N-CRM [Neuenschwander, 2008]. The FACTS will be used to conduct the N-CRM. These decisions will occur following review of these data by the investigator(s), GSK medical monitor, CPMS representative, and statistician. The decision and rationale will be documented in written format and distributed to the investigator(s), GSK medical monitor, CPMS representative, and statistician.
- Dose adjustments/stopping criteria will adhere to guidelines provided in Section 3.10.
- Subjects will receive GSK2857916 in this weekly dosing cohort until disease progression, unacceptable toxicity, withdrawal of consent, or completion of the pre-specified treatment period of 48 doses (16 cycles on Schedule 2).
- If a subject misses a dose on the weekly schedule, the dose will be recorded as missing and the next dose will be administered according to the current cycle. The counting of days and cycles will continue regardless of whether or not the subject received the dose. Dose delays of + 3 days are allowed in order to accommodate scheduling conflicts/holidays, etc.

Additional alternative schedules may be evaluated based on emerging data. If an alternative schedule other than the weekly dosing schedule is evaluated, details on dosing and Time and Events will be updated in the Study Procedures Manual (SPM).

3.3.3. Dose-Limiting Toxicity - Part 1 only

Any subject in Part 1 (Dose Escalation) who received at least one dose of the drug (regardless of schedule) will be evaluated for DLTs. Safety data together with DLTs will be reviewed during the dose escalation meetings prior to opening enrollment into subsequent cohorts (see Section 12.1).

Subjects who have been withdrawn from the study for reasons other than toxicity but prior to completion of DLT observation period will be replaced. An event will be considered a DLT if its relationship to the investigational agent cannot be ruled out occurs within the DLT reporting period (first 21 days of treatment for schedule 1, and first 28 days for schedule 2) and meets one of the following criteria:

- Albuminuria ≥ 2000 mg/24 hr which has been confirmed by repeat test at least 7 days apart and is not considered to be related to disease progression based on consultation of investigator with GSK medical monitor
- Grade 4 neutropenia (without fever) lasting ≥ 7 days
- Febrile neutropenia lasting ≥ 72 hours
- Grade ≥ 3 thrombocytopenia associated with bleeding where estimated blood loss is > 10 mL or Grade 4 thrombocytopenia lasting > 7 days and not responding to platelet transfusions
- Any Grade 3 or greater non-hematologic toxicity as described in Common National Cancer Institute-Terminology Criteria for Adverse Events (NCI-CTCAE) version 4.0 [NCI, 2009] with the exception of the following Grade 3 events that can be controlled within 48 hours with routine supportive measures
 - Nausea and vomiting that can be controlled with anti-emetics
 - Diarrhea that can be controlled with anti-diarrheals
 - Rash or other skin reactions that can be controlled with antihistamines and steroids
 - Clinically asymptomatic electrolyte abnormalities which can be corrected within 48 hours)
- Liver toxicity meeting pre-specified GSK liver stopping criteria (see Liver in Section 3.9.1)

Tumor lysis syndrome does NOT constitute a DLT (Section 3.9.7).

A subject who develops a DLT will be allowed to stay on study only if the toxicity did not meet stopping criteria and recovered to \leq Grade 1 within 14 days, or after a longer recovery time if benefit to subject can be demonstrated and if the investigator and medical monitor agree that for a given subject the benefits may outweigh the risks.

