3.3.1.1. Single Subject Cohort Run-in (Schedule 1 only)

- A single subject will be enrolled at each dose level as outlined in Table 4 until occurrence of a \geq Grade 2 toxicity for which relationship to the investigational agent cannot be ruled out.
- Initially, GSK2857916 will be administered (IV) via 60 min infusion once every three weeks (21 days = 1 cycle) on Schedule 1. One subject or the sentinel subject i.e., the very first subject on the study; will initially be enrolled at the starting dose of 0.03 mg/kg in Cohort 1 (Refer to Section 3.6.4 for starting dose rationale). The initial dose will be given to the sentinel subject. Serial blood samples will be collected for PK. The sentinel subject must remain under observation for at least 24 hours after dosing before discharge. GSK2857916 (intact and total [intact + unconjugated antibody]) and cys-mcMMAF plasma concentrations will be analyzed and reviewed together with the safety data (DLT period). If the first dose is considered tolerated, the sentinel subject will be allowed to stay on the study and receive subsequent doses at the same dose level (i.e., 0.03 mg/kg) as scheduled, every three weeks (21 days interval) for up to 16 doses (or until disease progression, toxicity or withdrawal of consent).
- If the sentinel subject does not experience a \geq Grade 2 toxicity for which relationship to the investigational agent cannot be ruled out during the first cycle (within 21 days), the next subject will be allowed to enroll in the next cohort at a dose increased by $\leq 100\%$ of the starting dose. Dose escalation with increments up to 100% of the previous dose will continue with enrolment of 1 subject per cohort until the occurrence of the first \geq Grade 2 toxicity for which relationship to the investigational agent cannot be ruled out. (run in procedure outlined in Table 4)
- The single subject (small cohort) run-in will be halted when the first \geq Grade 2 toxicity for which relationship to the investigational agent cannot be ruled out occurs in one subject in Cycle 1 (21 days). At this point, the cohort will be expanded to 3 or more subjects at the same dose level and the escalation will continue to follow the N-CRM procedure as outlined in Table 4

Table 4 Single Subject (Small Cohort) Run-In Procedure for GSK2857916 given on Schedule 1 (once every 21 days)

Dose Level	Number of subjects with \geq G2 toxicity	Dose Escalation/Action

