Dose Level 1/Cohort 1	0 out of 1 subject (Sentinel subject)	Predicted starting dose 0.03 mg/kg every 21 days
Dose Level 2/Cohort 2	0 out of 1 subject	Escalate to the next dose level with increase \leq 100% of the starting dose
Dose Level 3 and beyond/Cohort 3 and beyond	0 out of 1 subject	Escalate to the next dose level with increase of \leq 100% of the dose tested in the previous cohort
	1 out of 1 subject*	Switch to Cohort size of 3 or more subjects

*Increase of doses **up to** 100% of the previous dose may continue until the first \geq Grade 2 toxicity for which relationship to the investigational agent cannot be ruled out occurs in one subject in Cycle 1 (21 days). At this point the single subject (small cohort) run-in is halted. Continue with N-CRM, with cohort sizes of 3 or more subjects. Increase of doses \leq 100% will be considered for subsequent cohorts of 3 or more subjects.

- Dose escalation/de-escalations decisions will take into account all available data, including but not limited to the safety parameters, PD and PK data of all cohorts assessed. Dose escalation/de-escalation decisions will be informed by the N-CRM [Neuenschwander, 2008]. The N-CRM model used for Schedule 1 is described in detail in Section 3.3.1.2. The method is fully adaptive and makes use of all DLT information available at the time of each dose assignment. The Fixed and Adaptive Clinical Trial Simulator (FACTS) will be used to conduct the N-CRM. Dose-related decisions will occur following review of these data by the investigator(s), GSK medical monitor, clinical pharmacology modelling and simulation (CPMS) representative, and statistician. The decision and rationale will be documented in written format and distributed to the investigator(s), GSK medical monitor, CPMS representative, and statistician.
- The MTD will be defined as that dose which has the highest probability of having a DLT rate within the target toxicity interval, and for which the probability that the DLT rate lies within the excessive toxicity or the unacceptable toxicity window is less than 25% (see Section 3.3.3 for DLT definitions). The DLT assessment period on Schedule 1 will be 21 days.
- Dose adjustments/stopping criteria will adhere to guidelines provided in Section 3.10.1.

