19. Collect cytokines at predose (within 30 minutes prior to SOI) and EOI (± 5 min) (even when infusion is interrupted or halted) to assess allergic reaction)
20. All ADA samples will be collected prior to each infusion
21. PK samples to be taken (in all subjects) for both GSK2857916 and cys-mcMMAF measurement: C1D1 at pre-dose (within 30 minutes prior to SOI), 0.5 h after the start of the infusion (SOI) (± 5 min), at the end of infusion (EOI) just before EOI, 1 h after EOI, 3 h after EOI (± 5 min), 8 h after EOI (± 15 min), 24h after EOI (± 1 h) (Day 2); C1D8 1 sample; C1D15 1 sample; C2D1, at pre-dose (within 30 minutes prior to SOI) and at the EOI (just before EOI); C3D1 at pre-dose (within 30 minutes prior to SOI) and at the EOI (just before EOI).
22. Collect 1 PK sample at each subject's final visit.
23. Pre-specified amounts of urine will be collected for PK analysis from the 24 hour urine collection at Screening, C2D1, C4D1, C7D1, C10D1, C13D1, and C16D1. Refer to Section 7.4.2 for details.
24. Study drug administration ± 3 day window only
25. Prophylaxis with prednisolone phosphate 1% or dexamethasone 0.1% 1 drop QID x 4 days starting 1 day prior to treatment
26. Record subject's survival status and whether subsequent treatment for disease was given. Subject does not need to come in for visit.

Abbreviations:

ADA = Antibody Drug Antibody; ALP = alkaline phosphatase; BCVA = best corrected visual acuity; BNP = B-type natriuretic peptide; C1D1 = Cycle 1 Day 1, etc.; cfDNA = Circulating free DNA; CK = creatinine kinase; CRP = C-reactive protein; EM = extramedullary; EOI = End of Infusion; FLC = free light chain; PD = Pharmacodynamics; PK = Pharmacokinetics; QID = 4 times a day; SOI = start of infusion; SPEP = serum protein electrophoresis; UPEP = urine protein electrophoresis

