7.7. Evaluation of Anti-Cancer Activity

Standard disease assessments for MM will include laboratory tests, bone marrow aspirate (cytology, flow cytometry, FLC, etc.) and Bone Marrow biopsy for BCMA expression (IHC) during screening and at the time of CR. Evaluation will be according to the International Myeloma Working Group Uniform Response Criteria for Multiple Myeloma ([Appendix 1](#)). Disease assessment for subjects with lymphomas will be evaluated at screening and every 9 weeks (for subjects on every 3 week dosing schedule) or every 8 weeks (for subjects on weekly dosing schedule), and at the end of study. Disease assessment for subjects with lymphomas will be according to the Revised Response Criteria for Malignant Lymphoma ([Appendix 2](#)).

- Clinical activity measured as Overall Response Rate (ORR) which is defined as follows:
 - For MM: the percentage of subjects with confirmed stringent complete response (sCR), complete response (CR), very good partial response (VGPR), and partial response (PR) as assessed by 2011 recommendation of the International Myeloma Working Group (IMWG) Panel I ([Appendix 1](#)). Other comparisons of interest may be considered (see Section [13.5.2](#))

- For lymphomas: the percentage of subjects with confirmed CR, PR, as described in the Revised Response Criteria for Malignant Lymphoma ([Appendix 2](#)).

Disease assessment may include imaging (e.g., computed tomography [CT] scan, magnetic resonance imaging [MRI], bone scan, plain radiography) and physical examination (as indicated for palpable/superficial lesions). Disease assessment will be completed within 4 weeks prior to the first dose of GSK2857916 then every 8 or 9 weeks thereafter, and at the final study visit. See the Time and Events Tables (Section 7.1) for the schedule of assessments of anti-cancer activity. Assessments must be performed on a calendar schedule and should not be affected by dose interruptions/delays. For post-baseline assessments, a window of ± 3 days is permitted to allow for flexible scheduling with the exception of dose administration days where a window of ± 3 days for Schedule 1 (once every 3 weeks) is permitted and ± 1 day for Schedule 2 (weekly) is permitted. If the last radiographic assessment was more than 8 or 9 weeks prior to the subject's withdrawal from study and progressive disease has not been documented, a disease assessment should be obtained at the time of withdrawal from study.

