12.1. Data Dissemination and Communication Plan

The GSK Medical Monitor will review screening packets to ensure that subjects being considered for enrolment meet eligibility criteria prior to entering the study. Subjects will not be assigned a study number until their screening packet is reviewed and approved by the GSK Medical Monitor. GSK will remain in constant contact with the clinical sites during the enrolment period to ensure that cohort enrolment in Parts 1 and 2 of this study are completed as per protocol. Investigators will be informed about available openings for enrolment on the trial and will be asked to pre-screen their subjects to determine potential eligibility, and to avoid over-enrolment. Enrollment will be offered to a given site for a limited period of time, and if the site chosen cannot successfully enrol a subject within a pre-specified time period then another site will be offered the opportunity to enrol a subject.

During Part 1 of the study, Study Team Safety Update Meetings will be held every three weeks to review relevant data with the Principal Investigators (or delegates) and site staff. These meetings will be held on an “as needed” basis (but no less frequent than once a month) during Part 2 (e.g., to share safety experience and to communicate results of scheduled futility analyses). Safety, PK, PD, and clinical outcome data available for all subjects at the time of the scheduled Safety Update Meeting will be reviewed and summarized. In addition, Dose Escalation Meetings will be scheduled at the conclusion of the DLT assessment period for subjects enrolled in each cohort to review safety PK, and PD data and determine the next dose level appropriate for study. Dose escalation decisions will be made with team and investigator agreement after review of available safety data from at least one cycle of therapy with GSK2867916 (i.e., 21 days for the once every 3 weeks schedule and 28 days for weekly schedule). All dose escalation or safety decisions will be documented in writing with copies maintained at each site and the Master Study Files at GSK. Available data will be provided to participants prior to each scheduled Safety or Dose Escalation Meeting.

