13.4.1. Analysis Populations

The ‘All Treated’ population is defined as all eligible subjects who receive at least 1 dose of study treatment. An incorrect treatment schedule or drug administration or an early termination of treatment will not result in exclusion of subjects from this population. Subjects with major deviations from the eligibility criteria affecting safety or from the treatment schedule at the DLT evaluation period (1 cycle: 21 days for once every 3 weeks schedule or 28 days for once weekly schedule) for reasons other than toxicity may be presented in separate tables/listings.

The ‘All Treated’ population will further be classified in the following sub-populations.

- Part 1: all Part 1 subjects of All Treated population. Note, subjects in Part 1 are exclusively multiple myeloma patients.
- Part 2 MM: all Part 2 MM subjects of All Treated population
- All Treated MM: comprise of subjects in Part 1 and Part 2 MM.
- Part 2 NHL: all Part 2 lymphoma subjects of All Treated population.

The ‘**DLT Evaluable**’ population in Part 1 enables an appropriate evaluation of study DLTs. It is defined as those subjects fulfilling the ‘All Treated’ population criteria, and having met the following adequate exposure criteria:

- For Schedule 1 (once every 3 weeks dosing) subjects received a complete infusion in cycle 1.
- For Schedule 2 (once weekly dosing for 3 consecutive weeks, 1 week rest) subjects receive three infusions, two of which must be complete infusions, in cycle 1. (as increases up to $\leq 30\%$ are implemented between cohorts, less than 2 complete infusions would result in a total dose closer to the previous dose investigated).

Any subject in the “All Treated” population who experiences a DLT, as defined in Section 3.3.3 will also be included in the DLT evaluable population regardless of exposure.

The ‘**Evaluable (MM)**’ population is a subset of the ‘All Treated’ population, who were initially treated at RP2D in the expansion cohort and have at least two post-baseline disease assessments or they have progressed or died or permanently discontinued treatment. This population will be used for the futility analysis of the MM expansion cohort.

The ‘**Pharmacokinetic (PK) Population**’ is defined as those subjects in the “All Treated” population from whom at least one PK sample was obtained, analyzed, and was measurable.

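### Part 1, Schedule 1: the ±3 day dosing window lets the second infusion of a non-sentinel subject fall on Days 19-21, inside the fixed 21-day DLT period; a small effect that is cheap to remove

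*Protocol*

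**What the plan says.** - **DLT period.** Section 3.3.3 counts an event as a DLT if its relationship to the agent cannot be ruled out, it meets a listed criterion, and it occurs in the "first 21 days of treatment for schedule 1, and first 28 days for schedule 2". Section 3.3.1.1 repeats the length: "The DLT assessment period on Schedule 1 will be 21 days".
- **Dosing window.** Footnote 24 of the Part 1 every-3-weeks table (7.1.1.1), attached to the Cycle 2 Day 1 administration cell, reads "Study drug administration ± 3 day window only". Section 7.7 repeats it in its general window for post-baseline assessments, "with the exception of dose administration days where a window of" three days either side applies on Schedule 1 and one day on Schedule 2.
- **One cycle equated with 21 days.** Section 13.4.1 speaks of the "DLT evaluation period (1 cycle: 21 days for once every 3 weeks schedule" and, for Schedule 1, requires one complete Cycle 1 infusion for DLT evaluability. Section 12.1 bases escalation decisions on a meeting held "after review of available safety data from at least one cycle of therapy", given as 21 days. The run-in rule in 3.3.1.1 stops single-subject cohorts when a Grade 2 or greater toxicity "occurs in one subject in Cycle 1 (21 days").
- **Sentinel subject.** Section 3.3.1.1 makes further dosing conditional: "If the first dose is considered tolerated, the sentinel subject will be allowed to stay on the study and receive subsequent doses", at a 21-day interval, with safety data reviewed over the DLT period. No such condition is stated for later subjects.

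**The concern.** The N-CRM takes each subject's DLT status as the first-cycle outcome at the assigned dose, and the DLT Evaluable rule in 13.4.1 is built on one infusion in that cycle. The dosing window breaks the match between the cycle and the DLT period. Two subjects at the same dose can have one or two infusions within the 21 days, depending only on scheduling, and an acute reaction to the second infusion counts for one and not for the other.

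The event type is one the protocol plans for. Section 3.9.5 provides for infusion reactions at the first or any later infusion, and infusion reactions and cytokine release are not among the Grade 3 exceptions in 3.3.3. Section 13.4.1 puts any subject with a DLT into the DLT Evaluable population regardless of exposure. No rule lets the escalation meeting take a dose-2 event on Days 19-21 out of the DLT count. What is at stake is an occasional extra DLT in the model that sets the next dose and the MTD.

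**Working it through.** **1. Day count.** Day 1 is the first infusion. The protocol's treatment length confirms the 21-day cycle: 16 × 21 / 7 = 48 weeks, as stated in 3.3.1.1.

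**2. Overlap on Schedule 1.**
- Nominal Cycle 2 Day 1: 1 + 21 = Day 22.
- Permitted days: 22 − 3 = 19 to 22 + 3 = 25, which is 7 days.
- Inside the DLT period (Days 1-21): Days 19, 20 and 21, so 3 of 7. Outside: Days 22 to 25.
- With dosing on Day 19, Days 1-18 (18 days) follow dose 1 alone.

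**3. Overlap on Schedule 2.** Nominal Cycle 2 Day 1 is 1 + 28 = Day 29. Footnote 25 of 7.1.1.2 allows ±1 day, so Days 28-30, and Day 28 lies inside the 28-day period.

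**4. Expected number affected on Schedule 1.** The protocol gives no rate of early dosing or of first severe reactions at dose 2, so both are assumed:
- Share dosed on Days 19-21: 10% to 43% (3/7, infusions spread evenly over the window).
- Share with a first qualifying reaction at dose 2: 1% to 5%.
- Per-subject probability: 0.10 × 0.01 = 0.001 to 3/7 × 0.05 = 0.0214.
- Subjects: the simulated mean sizes in 13.2.1 run from 19.43 to 20.55; less the sentinel, 18.4 to 19.6, about 19. At the Schedule 1 ceiling of 30, 29.

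| Non-sentinel subjects | Low | High |
|---|---|---|
| 19 | 19 × 0.001 = 0.02 | 19 × 0.0214 = 0.41 |
| 29 | 29 × 0.001 = 0.03 | 29 × 0.0214 = 0.62 |

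For one affected subject to be expected among 29, even with 3/7 dosed early, the reaction rate would have to be (1/29) / (3/7) = 8.0%; among 19, (1/19) / (3/7) = 12.3%.

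**5. Can one event matter?** An illustrative N-CRM run used the prior in 13.2.1. The reference dose is not stated, so 0.96, 1.92 and 4.5 mg/kg were tried. The assumed history was 0 of 1 at each dose from 0.03 to 0.48 mg/kg and 0 of 3 at 0.96, then three subjects at 1.92. Recommended next dose (mg/kg):

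| DLTs at 1.92 | Ref. 0.96 | Ref. 1.92 | Ref. 4.5 |
|---|---|---|---|
| 0 of 3 | 3.6 | 3.6 | 3.6 |
| 1 of 3 | 2.8 | 3.6 | 3.6 |
| 2 of 3 | 1.92 | 1.92 | 2.8 |

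A first DLT changes the recommendation under one reference dose of three, and a second under all three. This shows that one extra DLT can matter, not that the overlap is likely to produce one.

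**The case against.** The strongest reply is that nothing is contradictory. Section 3.3.3 is a calendar rule that gives one answer for every dosing date, and any fixed cut-off separates Day 21 from Day 22. Relatedness is to the agent, not to dose 1, and Schedule 2 deliberately places three infusions inside its DLT period. A visit window exists for scheduling and does not falsify a nominal 21-day cycle. All of this stands. A reader might infer that 3.3.3 is ambiguous, or that a DLT must be attributable to the first infusion alone; the text supports neither. The run-in trigger is less clear: its wording can be read to include or to exclude an event after an early second infusion.

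Safeguards also exist. All 21 days are observed, escalation considers all available data including non-DLT events, and an extra DLT can only push the dose down. Dose 2 is normally the same assigned dose, because section 3.5 requires two completed cycles before intra-subject escalation. Section 3.9.6 considers acute allergic reactions unlikely. These points limit the effect but do not remove it: number of infusions in the DLT period still differs between subjects at one dose, and the model count has no provision for that.

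A reader might also take the upper assumptions as a forecast. With 19 or 29 subjects they give a 34% or 47% chance of at least one affected subject, but only if infusions are spread evenly over the window and a 5% reaction rate holds at every dose level, including the very low run-in doses, with nobody stopping before dose 2. Those figures are an extreme upper bound.

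**Conclusion.** The overlap is real and follows from the text: for non-sentinel Schedule 1 subjects, 3 of the 7 permitted Cycle 2 dosing days lie inside the DLT period, and no clause prevents or resolves it. Its effect is small. Fewer than one affected subject is expected throughout the assumed ranges (0.02 to 0.62), and any miscount is conservative. The day arithmetic rests on the protocol alone; the expected counts rest on assumed rates.

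Two stronger readings do not hold. The documents do not support saying that the MTD would be materially biased. Nor does the point extend to the sentinel subject, whose further dosing already depends on tolerating the first dose after DLT-period review. This is a refinement worth considering, not an error that endangers the design.

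**What to change.** In footnote 24 of 7.1.1.1, and for Part 1 in 7.7, set the Cycle 2 Day 1 administration window on Schedule 1 to 0/+3 days (Days 22-25). Leave the 21-day DLT period and the windows for later cycles unchanged. The number of permitted Cycle 2 dosing days inside the DLT period falls from 3 to 0.

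For Part 1 Schedule 2, state in footnote 25 of 7.1.1.2 only that the Cycle 2 Day 1 infusion may not be given before Day 29. Do not add an upper limit there, because section 3.3.2 already allows dose delays of up to 3 days.

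The cost is an edit to two footnotes and one clause, with no new visits or data. The downside is slightly less scheduling flexibility at one visit per Part 1 subject.
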